## 4.6.2 Time to onset of biological response of C-peptide following MMTT

The biological response of C-peptide is defined as a value >0.2 ng/mL for the C-peptide measurement. Time to onset of biological response of C-peptide will be calculated in two ways: the time to onset of biological response from implantation, and the time to biological response within each MMTT.

For the time to onset of biological response from implantation, the time unit will be 'days' and the time itself will be calculated as:

Time to onset of biological response of C-peptide (days) = (Date of first MMTT at which the subject achieved at least one C-peptide > 0.2 ng/mL) – (Date of surgical implantation procedure for the subject) + 1

For the time to onset of biological response within each MMTT, the time unit will be 'minutes' and the time itself will be calculated as:

Time to onset of biological response of C-peptide (minutes) = (Time during MMTT at which the subject first achieved a C-peptide > 0.2 ng/mL) –(Start time of Boost Hi-Protein drink for the MMTT for the subject)

For these time-to-event analyses, subjects who did not achieve biological response will be censored. That is, for the time to onset of biological response of C peptide from implantation, subjects who did not achieve at least one C-peptide > 0.2 ng/mL during any MMTT will be censored at the time they leave the study (complete the study, or withdrawal from the study).

For the time to onset of biological response within each MMTT, subjects who did not achieve at least one C-peptide within a 4-hour MMTT will be censored at 240 minutes. Subjects who did not achieve biological response of C-peptide during a 2-hour MMTT will be censored at 120 minutes.

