## **10.3.2.** Internal Efficacy and Safety Review

After the last subject in Cohort 2 passes Visit 11 (Week 26), cumulative data from all Cohort 1 and Cohort 2 subjects will be assembled and sent to the DSMB and Sponsor for review. If the Sponsor believes the efficacy data appear robust, and the DSMB believes the safety data are appropriate, the Sponsor may choose to proceed to an End-of-Phase 2 (EoP2) meeting with the FDA to discuss next steps.

The Sponsor will perform a risk/benefit assessment at 9-12 months post-implant for each Cohort 2 subject and at other time points, as warranted. This assessment evaluates each individual subject's data in order to determine whether that subject should continue taking chronic immunosuppression and remain in the study or whether all units will be explanted. Factors evaluated include C-peptide concentration, histology from a sentinel device explanted at approximately nine (9) months, change from baseline in average weekly insulin administration, change from baseline in HbA1c, change from baseline in frequency of hypoglycemic events, change from baseline in Clarke Score, change from baseline in time-in--range, compliance with immunosuppression, as well as adverse events and other safety findings. In cases where a subject is early terminated from the study as a result of the risk/benefit assessment, specific early termination visit procedures (i.e., the 4-hour MMTT and safety ultrasound) will not need to be repeated if they were recently performed (within the last 8 weeks).

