## 6.2 Secondary Efficacy Endpoints and Analyses

Each of the secondary efficacy endpoints will be analyzed using an  $\alpha = 0.05$  level of significance. Given the large number of secondary efficacy endpoints, the p-values for these endpoints will be considered descriptive.

For all secondary efficacy analyses, the FAS (Cohort 2 subjects who meet the FAS criteria) will be used. Change from baseline in C-peptide AUC0-4h following an MMTT at Weeks 52, 78, and 104 and change from baseline in C-peptide AUC0-2h following an MMTT at Weeks 8, 12, 16, 20, 39, 52, 65, 78, 91, and 104 will be analyzed in a similar manner to the ANCOVA performed for change from baseline in C-peptide AUC0-4h at Week 26, with the relevant baseline as the covariate. For subjects who continue to have a C-peptide  $\leq 0.1$  ng/mL as determined by the simplified oral glucose challenge test, the AUC of the respective 2-hour MMTT will be set to 0. A listing of the 2-hr MMTT/C-Peptide and Glucose results will be provided, as well as a listing of the simplified oral glucose challenge.

Time to onset of biological response of C-peptide following MMTT will be assessed using Kaplan-Meier (KM) product-limit method, with the p-value from the logrank test also provided.

The number and percent of subjects achieving a positive stimulated C-peptide (defined as > 0.2 ng/mL) after implant will be analyzed using Fisher's exact test. The number and percent of subjects in each treatment group and the p-value from the Fisher's test will be provided (at each time point, where appropriate).

Change from baseline in frequency of hypoglycemic events (24-hour; daytime [start between 6 a.m. -12 a.m.]; nocturnal [start between 12 a.m. -6 a.m.]) at Weeks 16, 26, 52, 78 will be analyzed using ANCOVA, with treatment group as a factor and the relevant baseline as a covariate. This analysis will be performed using HEs from both the patient-reported diary and from CGM. A listing of hypoglycemic events will be provided for both patient-reported data and from CGM data.

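### Censoring non-responders whose units have all been explanted makes the Kaplan-Meier curve for time to C-peptide response overstate, late in follow-up, the response achieved in the trial (minor)

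*SAP*

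**What the plan says.** SAP 4.6.2 sets the event: "The biological response of C-peptide is defined as a value >0.2 ng/mL for the C-peptide measurement". For time from implantation, "subjects who did not achieve at least one C-peptide > 0.2 ng/mL during any MMTT" are non-events, and they "will be censored at the time they leave the study", whether by completing it or by withdrawing. Completion and withdrawal are thus handled alike. SAP 6.2 names the method: "Kaplan-Meier (KM) product-limit method, with the p-value from the logrank test also provided". SAP 4.4, 4.6.2 and 6.2 contain no competing-risk method, no rule that keeps explanted subjects as non-responders, and no sensitivity analysis for this endpoint.

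Protocol 10.3.2 adds a step that the SAP does not mention: "The Sponsor will perform a risk/benefit assessment at 9-12 months post-implant for each Cohort 2 subject", and at other times if warranted. The outcome is either to remain in the study or to have all units removed. "Factors evaluated include C-peptide concentration" and histology of a sentinel explanted at about nine months. The list goes on to insulin use, HbA1c, hypoglycemic events, Clarke score, time in range, compliance with immunosuppression, and safety. Protocol 13.6 makes the result of this assessment a ground for withdrawal. Protocol 13.6.1 has units explanted at premature withdrawal and recognises insufficient response as a reason distinct from an adverse event. SAP 9.1 repeats the Week 26 review from Protocol 10.3.2 but leaves out the individual assessment.

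**The concern.** Kaplan-Meier treats a censored subject as one who could still have the event after censoring, at the same rate as those who remain at risk. A subject whose units have all been removed cannot respond to the product. Censoring that subject shifts the missing weight onto the non-responders who keep their units, so each later first response raises the curve by more than one subject's share.

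What is at stake is the late part of one secondary display. A reader would take the height of the curve at Week 104 as the share of subjects who responded, and it could be higher than that share. Two analyses are not touched. The primary endpoint is a Week 26 ANCOVA of AUC. The within-test time to response is censored at 120 or 240 minutes and has nothing to do with leaving the study.

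**Working it through.** **Is there a figure to reproduce?** No. The readable text gives no response rate, explant rate or event count for this endpoint, and the power text for the 40 subjects is blacked out. The rates below are assumptions, chosen to show a range.

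**Inputs from the documents.** N = 40 (SAP 10, optimized configuration). The individual assessment falls at 9 to 12 months (Protocol 10.3.2), roughly Weeks 39 to 52. Later tests are due up to Week 104 (SAP 4.6.1).

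**Assumed.** R = 20 responders by Week 39. W = non-responders with all units explanted after Week 39 and before the next first response. L = later first responders among those retained. There is no other loss before the end of study.

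**Formulas.**
- As planned: 1 − KM = 1 − (1 − R/N) × (1 − L/(N − R − W)).
- Cumulative incidence with explant as a competing event: CIF = (R + L)/N.
- Subtracting: excess = (L/N) × W/(N − R − W). This is never negative, and it is zero if W = 0 or L = 0.

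**Results for N = 40, R = 20.**

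| W | L | 1 − KM | CIF | Excess (points) |
|---|---|---|---|---|
| 5 | 4 | 1 − 0.5 × 11/15 = 63.3% | 24/40 = 60.0% | 3.3 |
| 10 | 2 | 1 − 0.5 × 8/10 = 60.0% | 22/40 = 55.0% | 5.0 |
| 10 | 4 | 1 − 0.5 × 6/10 = 70.0% | 24/40 = 60.0% | 10.0 |
| 15 | 4 | 1 − 0.5 × 1/5 = 90.0% | 24/40 = 60.0% | 30.0 |
| 5, 10 or 15 | 0 | 50.0% | 20/40 = 50.0% | 0 |

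With N = 60, R = 30, W = 15 and L = 6, the excess is (6/60) × 15/15 = 10 points.

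**Which quantity is overstated?** A simulation used 4,000 trials of 40 subjects on the SAP test schedule. It assumed 50% early and 15% late responders, so 65% would respond if nobody were explanted, and it varied the share of Week 39 non-responders explanted.

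| Selection for explant | Share explanted | 1 − KM | Response achieved |
|---|---|---|---|
| Random | 50% | 65.1% | 57.6% |
| Late responders weighted at one quarter | 25% | 68.2% | 63.6% |
| Late responders weighted at one quarter | 50% | 73.6% | 61.8% |
| Late responders weighted at one quarter | 75% | 83.1% | 58.4% |

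Under random selection, Kaplan-Meier recovers the hypothetical 65% but exceeds what was achieved. If selection favours keeping those with a better outlook, it exceeds both.

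**The case against.** The strongest reply is that Kaplan-Meier and cumulative incidence answer different questions. Everyone still at risk is a non-responder, so removal for non-response does not by itself separate the censored from the retained. The random-selection result bears this out: for the no-explant probability, Kaplan-Meier was unbiased. This stands. Bias against that target needs the further assumption that the assessment predicts later response. The listed C-peptide and histology make that plausible, but nothing in the documents shows it. However, the SAP does not declare a no-explant target, and against the response actually achieved the overstatement remains.

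The likely size may also be small. Protocol 2 expects maturation within three to six months, and the remark in Protocol 7.10 about later effect concerns insulin reduction, not the first value above 0.2 ng/mL. If few subjects first respond after the explants, the gap is close to zero. This stands as well.

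The plan also has partial safeguards. SAP 6.2 reports the number and percent with C-peptide above 0.2 ng/mL, SAP 5.1 tabulates withdrawals by reason, and secondary p-values are descriptive. A full-FAS percentage would show the final level but no time course, and it could disagree with the curve beside it.

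Two stronger readings are not supported. A reader might infer that subjects are explanted because they did not respond. Protocol 10.3.2 sets no C-peptide threshold and weighs several factors, and a subject who has passed 0.2 ng/mL but gained little clinically is already an event. A reader might also infer that the log-rank test is biased towards response. It compares groups defined by the number of VC-02-300 units initially implanted. With explants censored, it compares rates of first response among subjects who still carry units, which is a legitimate cause-specific comparison.

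**Conclusion.** The point holds in a limited form, and its severity is minor. As planned, 1 minus Kaplan-Meier is never below the response probability achieved in the trial, and exceeds it once any first response follows an explant of all units in a non-responder. The direction follows from the documents, but the size does not. Under the assumed rates above, the excess runs from 0 to 30 points. The 30-point case needs 15 of 20 non-responders explanted and 4 of the remaining 5 responding later, so it should be read as an extreme. Overstatement of the no-explant probability is conditional on the assessment selecting subjects with a poorer outlook. The curve before the first such explant is sound.

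**What to change.** In SAP 4.6.2 and 6.2, for time from implantation only:

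- Report the Aalen-Johansen cumulative incidence of first response, with explant of all units before response as the competing event, dated at that explant. The scheduled removal at Week 104 counts as completion.
- Keep ordinary censoring for completion and for subjects lost to contact with units still in place, since they could still respond unobserved.
- If groups are to be compared on cumulative incidence, add Gray's test. Keep Kaplan-Meier with log-rank as a sensitivity analysis labelled as cause-specific.
- State which probability the main curve estimates.

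The explant dates are already collected for the exposure summaries in SAP 7.1, so no new data are needed and no clinical rule changes. The cost is a few lines of SAP text, a little extra analysis, and a late response figure that may look less favourable.

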## 4.6.3 Frequency of hypoglycemic events using subject-reported diary data

HE data collected on the "Hypoglycemic Event" eCRF page will be used collectively for HE data summary and analysis. These data are collected from the subject-completed diaries. Hypoglycemic event logs will be completed via subject diary (via provisioned phones) by subjects. Investigators will review the hypoglycemic event logs completed by the subjects at each study visit. Blank values in the hypoglycemic events (HEs) log are considered to be 0 values.

HEs will be classified in six ways: total HEs, severe HEs, nocturnal HEs, severe nocturnal HEs, daytime HEs, and severe daytime HEs. Total HEs are HEs that occur at any time during the 24-hour period. Severe HEs (SHEs) are HEs requiring the aid of another person to administer carbohydrates, glucagon, or other resuscitative assistance any time during the 24-hour period.

Nocturnal HEs are HEs that start during the 12 a.m. - 6 a.m. period. Severe nocturnal HEs are SHEs that start during the 12 a.m. - 6 a.m. period. Daytime HEs are HEs that start during the 6 a.m. to 12 a.m. period. Severe daytime HEs are SHEs that start during the 6 a.m. to 12 a.m. period.

The baseline average weekly frequency of subject-reported HEs, SHEs, nocturnal HEs, severe nocturnal HEs, daytime HEs and severe daytime HEs will be calculated using up to 28 days of data. The baseline average weekly frequency will be calculated using data starting at Day -3 (i.e., the day prior to immunosuppression induction) and working backwards for up to 28 days (through Day -30). For instances in which the available pre-implant dataset provides <28 days of data, the dataset will be supplemented with post-implant data, using data from Day 4 forward until 28 days of data is available. Data from days on which an MMTT or SOGCT was performed will not be used in the calculation.

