### 7.10.4. Definition, Classification, and Management of Hypoglycemic Events (HEs)

All SMBG or CGM values of <54 mg/dL must be captured by the subject in the diary as a HE. Additionally, if a subject does not have a blood glucose value available, but has symptoms of a HE, the HE must still be captured in the diary as an HE. *For any SHE experienced between scheduled clinic visits, the subject must enter the data on the diary and also contact the study site to provide details of the event.* 

At Visit 3 (Day 1) and each clinic visit thereafter, the Investigator will review the subject's HE entries on the study diary, CGM and SMBG values, and any other supportive information. Each HE occurring beyond Visit 2 (Week -4) must be captured on a CRF and will be classified based on the definitions below. Per standards of care, the Investigator should also evaluate any HEs occurring between Visit 1 and Visit 2 reported by the subject, but they are not captured on the CRF.

- Severe hypoglycemic event (SHE): an event requiring assistance of another person to actively administer carbohydrate, glucagon, or other resuscitative actions.
- Documented symptomatic hypoglycemia: an event accompanied by typical symptoms of hypoglycemia with documented plasma glucose measured at <70 mg/dL (3.9 mmol/L).
- Asymptomatic hypoglycemia: an event with measured plasma glucose of <54 mg/dL (3.0 mmol/L) in the absence of symptoms.
- Probable symptomatic hypoglycemia: subject reports typical hypoglycemia symptoms but does not provide a temporally-associated SMBG or CGM value.
- Pseudo-hypoglycemia or relative hypoglycemia: an event is reported by subject, but the associated SMBG or CGM value is ≥70 mg/dL (3.9 mmol/L).

The frequency of HEs will be captured and counted over the course of the study. In addition, the Sponsor will consider defining additional HEs using the CGM data on an exploratory basis. The Investigator may request an Unplanned Visit to review study diary entries and determine if modifications in insulin dosing are necessary to reduce the occurrence of HEs. Based on available information, the Investigator should make appropriate decisions regarding the insulin therapy to mitigate HE occurrences.

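### SAP 4.6.3 applies no event-class filter, so diary events with glucose of 70 mg/dL or more count toward hypoglycemic event frequency

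*SAP*

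**What the plan says.** Protocol 7.10.4 sends every event to the CRF with a class: "Each HE occurring beyond Visit 2 (Week -4) must be captured on a CRF and will be classified based on the definitions below". The five classes are severe, documented symptomatic, asymptomatic (glucose below 54 mg/dL without symptoms), probable symptomatic (symptoms with no associated value), and pseudo- or relative hypoglycemia. Documented symptomatic is "an event accompanied by typical symptoms of hypoglycemia with documented plasma glucose measured at <70 mg/dL (3.9 mmol/L". Pseudo- or relative hypoglycemia is where "an event is reported by subject, but the associated SMBG or CGM value is ≥70 mg/dL (3.9 mmol/L".

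SAP 4.6.3 takes its data from the same form: "HE data collected on the 'Hypoglycemic Event' eCRF page will be used collectively for HE data summary and analysis". It then forms six categories from two attributes only, severity and clock time. For the total it says "Total HEs are HEs that occur at any time during the 24-hour period". The limits it sets are the windows (up to 28 days for baseline, 14 days before each later visit) and the removal of days with a mixed meal test or, at baseline, a glucose challenge.

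SAP 4.6.4 defines a second count from CGM: a set of readings below 70 mg/dL lasting at least 15 minutes, within which up to two consecutive readings at or above 70 are tolerated. SAP 6.2 analyses change from baseline in frequency by ANCOVA for both counts: "This analysis will be performed using HEs from both the patient-reported diary and from CGM". The p-values are descriptive.

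On diary entry, Protocol 7.10.4 says "All SMBG or CGM values of <54 mg/dL must be captured by the subject in the diary as a HE" and adds symptoms for which no glucose value is available. Protocol 7.10.1 separately requires daily entry of HE occurrences in general.

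**The concern.** The protocol separates out events whose measured glucose does not meet its own 70 mg/dL threshold, and the SAP then discards that separation. The diary version of a secondary efficacy endpoint would include events that could not qualify as an episode under the CGM version. If the two versions disagree, a reader could not tell a difference in data source from a difference in definition.

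The count is also subject-reported in an open-label trial whose hoped-for benefits include better awareness of hypoglycemia. How often subjects log symptoms at normal glucose could change after implantation for reasons unrelated to the number of low-glucose events. At stake is how the reported change in weekly HE frequency is read, overall and by day and night.

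**Working it through.** **1. Trace one record.** Take a subject-reported event after Visit 2 with an associated value of 85 mg/dL that did not need another person's help.

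- Protocol 7.10.4: it goes on the CRF, classed as pseudo- or relative hypoglycemia.
- SAP 4.6.3: it is on the eCRF page that is used collectively. If it falls in the window and not on an excluded test day, it adds one to the total and one to either the daytime or the nocturnal count. No glucose or class criterion removes it.
- SAP 6.2: no further filter.
- SAP 4.6.4: readings that stay near 85 mg/dL cannot form a CGM episode.

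**2. Effect on the planned scale.** The documents give no HE rates, so there is no plan figure to reproduce and the rates below are assumptions. Let T0 and T1 be the true weekly rates at baseline and follow-up, and P0 and P1 the pseudo rates.

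- Recorded change = (T1 + P1) − (T0 + P0) = true change + (P1 − P0).
- Counting variance of the change (Poisson, 4 weeks of baseline and 2 weeks of follow-up from the SAP windows) = (T0 + P0)/4 + (T1 + P1)/2.

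Assume T0 = 4 and T1 = 2, a true change of −2.00 per week. With no pseudo events, the SD is √(4/4 + 2/2) = 1.41. Let pseudo events be a share s of baseline records, so P0 = 4s/(1 − s).

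| s | P0 | P1 = P0: change (SD) | P1 = P0/2: change (SD) | P1 = 2 × P0: change (SD) |
|---|---|---|---|---|
| 10% | 0.44 | −2.00 (1.53) | −2.22 (1.49) | −1.56 (1.60) |
| 20% | 1.00 | −2.00 (1.66) | −2.50 (1.58) | −1.00 (1.80) |
| 30% | 1.71 | −2.00 (1.81) | −2.86 (1.69) | −0.29 (2.04) |

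With a constant pseudo rate the mean change stays at −2.00, and the counting SD rises from 1.41 to between 1.53 and 1.81. When the rate shifts, the mean change moves by exactly P1 − P0, toward zero if reporting rises and away from zero if it falls.

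**3. One worked shift.** If P0 = 0.5 and P1 = 1.5, the recorded rates are 4.5 and 3.5. The recorded change is −1.0 against a true −2.0, and the bias is 1.5 − 0.5 = +1.0 per week.

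**4. Diary entry rules.** The rule in Protocol 7.10.4 names values below 54 mg/dL and symptoms without a value. Its documented symptomatic class runs up to 70 mg/dL. Protocol 7.10.1 asks for all HE occurrences without saying what qualifies at 54 to 69 mg/dL. The three statements do not give a subject one consistent rule.

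**The case against.** The strongest reply is that the SAP follows the protocol. Protocol 7.10.4 lists pseudo- or relative hypoglycemia among its HE classes and then says HE frequency will be counted. The SAP nowhere says outright that these events are included. That is correct: inclusion is inferred from collective use of the page with no exclusion. It is still what a programmer would implement, and if exclusion was intended one sentence settles it.

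A second reply is that such records may be rare. No specific instruction tells a subject with symptoms at 85 mg/dL to log an event. This stands: their number is unknown. It also means the number depends on subject behaviour.

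A third is that the CGM analysis, which does not depend on symptoms, already serves as a check. That has force, but a check is easier to read when the two counts differ only in data source.

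Some stronger readings are tempting and not supported:

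- *That any real fall is diluted.* On a percentage scale, one constant pseudo event per week turns 4 to 2 (−50%) into 5 to 3 (−40%). The SAP analyses absolute change, which is −2 per week in both cases.
- *That improved awareness will read as more hypoglycemia.* The documents give no data on how pseudo reporting moves, and the bias can go either way.
- *That symptomatic events at 54 to 69 mg/dL have no capture instruction.* Protocol 7.10.1 requires HE occurrences to be logged, and the Investigator reviews diary, meter and CGM data at each visit. The rules are inconsistent rather than absent.
- *That the CGM rule rejects every reading at or above 70 mg/dL.* It tolerates up to two consecutive ones within an episode.

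**Conclusion.** The point holds as a definitional gap. As written, SAP 4.6.3 counts events the protocol classes as pseudo- or relative hypoglycemia toward total, daytime and nocturnal frequency. On the planned scale the cost is added noise if their rate is constant, and a bias equal to the change in their rate if it is not. The sizes above rest on assumed rates and Poisson counting error; only the direction of the argument comes from the documents.

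The change is worth making, but its reach is limited. It concerns one secondary endpoint with descriptive p-values in a study that tests no hypotheses. The C-peptide primary endpoint is unaffected, and diary severe events, defined by need for assistance, are not the target. A reader might infer that the main count should be cut back to the severe, documented symptomatic and asymptomatic classes. The documents do not support that: Protocol 7.10.4 requires symptomatic events without a glucose value to be captured as HEs.

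**What to change.** In SAP 4.6.3:

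- Exclude events classed as pseudo- or relative hypoglycemia from the total, daytime and nocturnal frequencies, at baseline and at follow-up alike.
- Keep the other classes in the main count, including probable symptomatic events.
- Tabulate HEs by protocol class at each analysed visit, so that any shift in pseudo reporting is visible.
- Add a sensitivity analysis that counts all records.

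In Protocol 7.10.4, reconcile the below-54 mg/dL diary-entry rule with the below-70 mg/dL documented symptomatic class and with the general logging duty in 7.10.1.

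The cost is SAP wording, one filter on a class the protocol already has assigned, one extra table and one sensitivity run, plus the protocol clarification. The filter will not remove every dependence on symptoms: an event at 60 mg/dL fits the documented symptomatic class if felt, but not the asymptomatic class if unfelt. The CGM count remains the useful companion for that reason.
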